3.6. Pooling of Centers

Summaries will be provided pooled for all sites overall and by group if not indicated otherwise.

4. Subject Characteristics

4.1. Subject Disposition

Summary table reflecting subject disposition will present:

- Number of enrolled subjects (only for overall).
- Number of non-eligible subjects (any eligibility criteria not met) [only for overall].
- Number of subjects by reason for ineligibility (only for overall): inclusion criteria not met; exclusion criteria met.
- Number (%) of eligible subjects.
- Number (%) of subjects who completed the study.
- Number (%) of subjects who discontinued the study with reasons for early study termination.
- Length of follow-up (days).
- Number (%) of subjects included in each analysis set (FAS and PP).

Supportive listings will be provided for subject disposition and study visits.

Derivations:

- Length of follow-up (days) = end of study date – date of first dose of study treatment + 1.

Note: For subjects who are still ongoing in the study at the time of the analysis, the end of study date will be imputed as the data cut-off date.

4.2. Protocol Deviations

Analysis Set: FAS

Protocol deviations will be identified periodically throughout the study based on the “Protocol Deviation Criteria Form”. This form is transferred before each analysis indicating subject with protocol deviations as reason of exclusion from PP. Major protocol deviations that lead to the exclusion from PP will be summarized. All protocol deviations will be listed.

4.3. Demographics and Clinical Characteristics at Baseline

Analysis Set: FAS

Demographic and clinical characteristics at Baseline will be summarized using the information collected from the screening data. Demographic and clinical characteristics will include:

- Age (years).
- Age categories: ≥ 18 years to < 30 years, ≥ 30 years to < 50 years, ≥ 50 years to < 70 years and ≥ 70 years.
- Sex: Male, Female, Unknown, Unconfirmed.
- Race: American Indian or Alaska Native, Asian, Black or African American, Native Hawaiian or other Pacific Islander, White, Other, Unknown, Unconfirmed.
Note: An additional category “Mixed” will be created for subjects with more than one race reported.
- Ethnicity: Hispanic or Latino, Not Hispanic or Latino, Unknown, Unconfirmed.
- IDEEL-SB symptoms score (only Group 1).
- CLDEQ-8 score (only Group 2).
- [REDACTED]
- BCVA score (logMAR) [eye-level summary].

A supportive listing for demographic and clinical characteristics will be provided.

4.4. Targeted Medical History

Medical conditions within 1 year prior to the Screening (Visit 1) will be collected from “Targeted Medical History and Concomitant Medication” eCRF form.

Any preexisting medical conditions or signs/symptoms present in a subject prior to the start of the study (i.e., before IC is signed) are not considered AEs in the study and should be recorded in the Medical History section of the eCRF.

A supportive listing for medical history will be provided.

4.5. Targeted Concomitant Medication

Concomitant medications taken within the past 30 days prior to the Screening/Baseline (Visit 1) will be listed.

4.6. Treatment Duration and Missed Doses

The frequency (number and percentage) of subjects with at least one missed dose during the study and the treatment duration (in days) will be summarized.

Derivations:

- Treatment duration (days) = date of last dose of study treatment – date of first dose of study treatment + 1.

Note: For treatment duration calculation, if the date of last dose of study treatment is unknown at the time of the analysis, it will be imputed as the end of study date (for subjects who complete or discontinue the study at the time of the analysis) or the data cut-off date (for subjects who are still ongoing in the study).

5. Efficacy Analysis Strategy

This study defines one primary effectiveness endpoint [REDACTED]
[REDACTED] The FAS will be used for all effectiveness analyses. The PP population will be the supportive analysis set for primary [REDACTED] analyses.

All endpoints will be summarized overall and by groups as defined in [Section 3.1](#).

No imputation for missing values will be carried out for the primary and supportive effectiveness analyses.

5.1. Efficacy Endpoints

PRIMARY EFFECTIVENESS ENDPOINT:

The primary effectiveness endpoint is:

- Group 1: Dry eye (DE) questionnaire via IDEEL-SB at Baseline and at Visit 3
- Group 2: DE questionnaire via CLDEQ-8 at Baseline and at Visit 3

5.2. Efficacy Hypotheses

There are no statistical hypotheses in this study.

5.3. Statistical Methods for Efficacy Analyses

5.3.1. Primary Effectiveness

Group 1:

DES will be assessed using the IDEEL-SB questionnaire (see [Appendix 13.2](#)) at the Screening/Baseline visit (Day 1) before Systane Ultra PF use, and at Visit 3 (and at unscheduled and at early exit visits, as necessary).

The primary effectiveness endpoint is the IDEEL-SB score. The IDEEL-SB score is calculated by the mean value of the non-missing item scores multiplied by 25, with a higher score indicating greater satisfaction and less treatment-related bother.

The primary effectiveness endpoint will be summarized as a continuous variable at each analysis visit (Baseline and Visit 3). The mean IDEEL-SB score will be presented together with the corresponding 95% CI.

Group 2:

CL symptoms will be assessed using the CLDEQ-8 questionnaire (see [Appendix 13.3](#)) at the Screening/Baseline visit (Day 1) before Systane Ultra PF use, and at Visit 3 (and at unscheduled and at early exit visit, as necessary).

[figure not shown]
The primary effectiveness endpoint is the CLDEQ-8 score. The CLDEQ-8 score is calculated by the sum of the non-missing item questions.

The primary effectiveness endpoint will be summarized as a continuous variable at each analysis visit (Baseline and Visit 3). The mean CLDEQ-8 score will be presented together with the corresponding 95% CI. [REDACTED]

Derivations:

- IDEEL-SB score = (Sum of (Item 1,..., Item 20) / n) x 25, where n = number of items with non-missing answer.
- CLDEQ-8 score = Sum of (Question 1,..., Question 8).

A large rectangular area of the page is completely blacked out, indicating that the original content has been redacted.

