7.3.3.1 IDEEL-SB (Group 1)

Dry eye symptoms will be assessed using the IDEEL-SB questionnaire (see Appendix 17.2.1) at the Screening/Baseline visit (D1), before Systane Ultra PF use, and at Visit 3 (and at unscheduled and at early exit visit, as necessary).

The IDEEL-SB (Version 1) symptom bother module consists of 20 questions that assess general dry eye symptoms a subject experiences. It should be administered prior to performing any other study testing procedure. The subject's response to each question will be entered on paper and scored to determine the eligibility of the subject to participate in the study.

Administration and Scoring

A paper copy of the IDEEL-SB module will be given to each subject for completion without assistance. All questions should be answered by the subject so please check the questionnaire before the subject leaves the study visit.

Question 1 is scored on a 5-point Likert-type scale where 0 = None of the time, 1 = A little of the time, 2 = some of the time, 3 = Most of the time, and 4 = All of the time. Questions 2-20 are scored on a 4-point Likert-type scale where 0 = I did not have this symptom / Not Applicable, 1 = Not at all, 2 = Slightly, 3 = Moderately, 4 = Very much.

The subject will be instructed to select a single response that best represents their answer. The score is calculated if at least 50% (10 items) of the 20 items within the dimension are completed; non-missing; otherwise the score is set to missing. The Symptom Bother score is calculated as the mean value of the non-missing item scores 1-20 multiplied by 25.

[figure not shown]
$$\frac{\text{Sum of responses from questions 1- 20}}{\text{Number of questions (1-20) answered}} \times 25 = \text{IDEEL SB score}$$

The final calculated IDEEL-SB score for each patient will be entered into the study source documents to determine eligibility at the Screening Visit.

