12.2. IDEEL-SB Questionnaire

Symptom Bother

These questions ask about the symptoms you may experience due to dry eyes.

1. **OVER THE LAST TWO WEEKS**, how often did you experience dry eye symptoms?

None of the time	A little of the time	Some of the time	Most of the time	All of the time
				

The following questions ask about how bothersome dry eye symptoms were to you **OVER THE LAST TWO WEEKS**. If you had the symptom, please choose **how much the symptom bothered you** (not at all, slightly, moderately, or very much). If you did not have the symptom over the last week, choose the "I did not have this symptom / Not applicable" box. Please choose only one box per question.

OVER THE LAST TWO WEEKS , how much did each of the following symptoms bother you?	I did not have this symptom / Not applicable	OVER THE LAST TWO WEEKS, I had this symptom and it bothered me:			
		Not at all	Slightly	Moderately	Very much
2. Eyes that felt gritty or sandy					
3. Felt like I needed to close my eyes even though I was not tired					
4. Burning or stinging eyes					
5. Tired eyes					
6. Blurry vision					
7. Itchy eyes					
8. Irritated eyes					
9. Eyes that felt like they had been scratched by something					
10. Eye dryness					

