OVER THE LAST TWO WEEKS , how much did each of the following symptoms bother you?	I did not have this symptom / Not applicable	OVER THE LAST TWO WEEKS, I had this symptom and it bothered me:			
		Not at all	Slightly	Moderately	Very much
11. Mucus in, around, or coming out of my eyes					
12. Puffy or swollen eyes					
13. Eye redness					
14. Aching or sore eyes					
15. Felt like something was in my eye					
16. Frequent and/or rapid blinking					
17. Difficulty blinking because of little or no moisture in my eyes					
18. Sensitivity to light, glare, and/or wind					
19. Sensitivity to re-circulated air (such as air conditioning and heat)					
20. Headaches associated with dry eye symptoms					

Thank you for finishing this questionnaire.
Please make sure that you answered every question.

Administration and Scoring

A paper copy of the IDEEL-SB module will be given to each subject for completion without assistance.

Question 1 is scored on a 5-point Likert-type scale where 0 = None of the time, 1 = A little of the time, 2 = some of the time, 3 = Most of the time, and 4 = All of the time. Questions 2-20 are scored on a 4-point Likert-type scale where 0 = I did not have this symptom / Not Applicable, 1 = Not at all, 2 = Slightly, 3 = Moderately, 4 = Very much.

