The subject will be instructed to select a single response that best represents their answer. The score is calculated if at least 50% (10 items) of the 20 items within the dimension are completed; non-missing; otherwise the score is set to missing. The Symptom Bother score is calculated as the mean value of the non-missing item scores 1-20 multiplied by 25.

$$\frac{\text{Sum of responses from questions 1- 20}}{\text{Number of questions (1-20) answered}} \times 25 = \text{IDEEL SB score}$$

The final calculated IDEEL-SB score for each subject will be entered into the study source documents to determine eligibility at the Screening Visit.

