Table 14.1.3.1.1: Summary of Demographics and Baseline Clinical Characteristics – FAS

Table 14.1.3.1.2: Summary of Demographics and Baseline Clinical Characteristics by Site – FAS

Table 14.1.4.1: Summary of Treatment Duration and Missed Doses – FAS

Table 14.2.1.1.1.1: Summary of IDEEL-SB Score by Analysis Visit (Group 1) – FAS

Table 14.2.1.1.1.2: Summary of IDEEL-SB Score by Analysis Visit (Group 1) – PP

Table 14.2.1.2.1.1: Summary of CLDEQ-8 Score by Analysis Visit (Group 2) – FAS

Table 14.2.1.2.1.2: Summary of CLDEQ-8 Score by Analysis Visit (Group 2) – PP

Table 14.3.1.1: Overall Summary of Non-Ocular Treatment-Emergent Adverse Events (TEAEs) - FAS

Table 14.3.1.2.1: Summary of Non-Ocular Treatment-Emergent Adverse Events (TEAEs) by MedDRA PT – FAS

Table 14.3.1.2.2: Summary of Serious Non-Ocular Treatment-Emergent Adverse Events (TEAEs) by MedDRA PT – FAS

Table 14.3.1.2.3: Summary of Non-Ocular Treatment-Emergent Adverse Events (TEAEs) Related with Study Device by MedDRA PT – FAS

Table 14.3.1.3: Overall Summary of Ocular Treatment-Emergent Adverse Events (TEAEs) - FAS

Table 14.3.1.4.1: Summary of Ocular Treatment-Emergent Adverse Events (TEAEs) by MedDRA PT – FAS

Table 14.3.1.4.2: Summary of Serious Ocular Treatment-Emergent Adverse Events (TEAEs) by MedDRA PT – FAS

Table 14.3.1.4.3: Summary of Ocular Treatment-Emergent Adverse Events (TEAEs) Related with Study Device by MedDRA PT – FAS

Table 14.3.2.1: Summary of BCVA Score (logMAR) by Analysis Visit – FAS

Table 14.3.3.1: Summary of Biomicroscopy Findings by Analysis Visit – FAS

Table 14.3.3.2: Shift from Baseline to Visit 3 Biomicroscopy Findings – FAS

Table 14.3.3.3: Summary of Corneal Staining by Analysis Visit – FAS

Table 14.3.3.4: Shift from Baseline to Visit 3 Corneal Staining – FAS

Table 14.3.3.5: Summary of Corneal Infiltrates by Analysis Visit (Group 2) – FAS

Table 14.3.4.1: Summary of Device Deficiencies - FAS

Listing 16.2.1.1: Listing of Subject Disposition

Listing 16.2.1.2: Listing of Missed Visits – FAS

Listing 16.2.2.1: Listing of Protocol Deviations – FAS

Listing 16.2.3.1: Listing of Demographics and Baseline Clinical Characteristics – FAS

Listing 16.2.3.2: Listing of Medical History and Concomitant Medication – FAS

Listing 16.2.3.3: Listing of Missed Doses - FAS

Listing 16.2.4.1: Listing of IDEEL-SB Questionnaire (Group 1) – FAS

■■■■■
Listing 16.2.4.3: Listing of CLDEQ-8 Questionnaire (Group 2) – FAS

■■■■■

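### SAP 5.3.1 states the direction and meaning of the Group 1 primary score (IDEEL-SB) wrongly: under the SAP's own scoring, a higher score is worse

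*SAP*

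**What the plan says.** SAP 5.3.1 names the IDEEL-SB score as the Group 1 primary effectiveness endpoint and defines it as the mean of the answered items times 25, "with a higher score indicating greater satisfaction and less treatment-related bother". The derivation at the end of the same section is "IDEEL-SB score = (Sum of (Item 1,..., Item 20) / n) x 25, where n = number of items with non-missing answer". The score is to be summarised as a continuous variable at Baseline and Visit 3, with a 95% CI for the mean.

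SAP 12.2 holds the questionnaire and its scoring:

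- Its introduction reads "These questions ask about the symptoms you may experience due to dry eyes".
- Item 1 asks how often symptoms occurred. Its codes start at 0 for no time and end with "3 = Most of the time, and 4 = All of the time".
- Items 2 to 20 ask how much each symptom bothered the subject. They start at "0 = I did not have this symptom / Not Applicable, 1 = Not at all" and rise to 4 for the strongest bother.
- The scoring rule is "The Symptom Bother score is calculated as the mean value of the non-missing item scores 1-20 multiplied by 25".

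Protocol 7.3.3.1 gives the same coding, with "1 = Not at all, 2 = Slightly, 3 = Moderately, 4 = Very much" above the zero category. It contains no sentence equivalent to the clause in SAP 5.3.1.

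**The concern.** The clause and the coding cannot both be right. If larger item codes mean more frequent or more bothersome symptoms, and the score is their unreversed mean, a larger score cannot indicate a better state. Nor can it indicate satisfaction or bother from treatment, because the items cover neither.

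This matters because of the endpoint concerned. The study has one arm, no comparator and, under SAP 5.2, no hypothesis. The visible Group 1 effectiveness result is two means with confidence intervals, and the reader's conclusion depends on which way the mean moved. An author or reader who relied on the clause would report improvement as deterioration, or the reverse.

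Checking the clause against the scoring is also harder than it should be. SAP 5.3.1 sends the reader to Appendix 13.2, but the questionnaire and scoring are in 12.2, and Section 13 is the list of outputs.

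**Working it through.** **Inputs**

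- Item codes: 0 to 4 for all 20 items, rising with symptom frequency (item 1) or bother (items 2 to 20). Source: SAP 12.2 and Protocol 7.3.3.1.
- Formula: score = (sum of answered items / number answered) × 25. Source: SAP 5.3.1 and 12.2.
- Completeness rule: at least 10 of 20 items answered. Source: SAP 5.4 and 12.2.
- Entry range for Group 1: above 16 and up to 64, labelled mild to moderate dry eye. Source: Protocol 6.4.4.

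The plan gives no expected IDEEL-SB value to reproduce. Its only sample-size figure is the half-width of 0.060 for an adverse-event proportion of 0.0543 with 54 subjects. That figure does reproduce, 1.96 × √(0.0543 × 0.9457 / 54) = 0.0604, and it does not depend on this score.

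**Step 1. Range and direction, all 20 items answered**

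| Every item coded | Sum | Score |
|---|---|---|
| 0 | 0 | (0/20) × 25 = 0 |
| 1 | 20 | (20/20) × 25 = 25 |
| 2 | 40 | (40/20) × 25 = 50 |
| 3 | 60 | (60/20) × 25 = 75 |
| 4 | 80 | (80/20) × 25 = 100 |

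A subject with no symptoms scores 0. A subject with symptoms all the time, each bothering very much, scores 100. The clause would describe that second subject as the most satisfied.

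**Step 2. Effect of one response category**

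Moving one item up one category adds 25/n points: 25/20 = 1.25 with all items answered, and 25/10 = 2.5 at the 10-item minimum. The change is always upward for a worse response, because no item is reverse-coded. The direction therefore holds for every permitted pattern of missing items.

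**Step 3. Illustration (assumed answers, not from the documents)**

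All items at 2 at Baseline gives 50; all items at 1 at Visit 3 gives 25. The change is 25 − 50 = −25. Under the coding, every symptom is one category milder, which is an improvement of 25 points. Under the clause, it is a loss of 25 points.

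**Step 4. Consistency with the entry range**

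The limits 16 and 64 correspond to mean item codes of 16/25 = 0.64 and 64/25 = 2.56. Requiring a score above 16 for dry eye to be present, and capping it at 64 for mild to moderate disease, fits a scale on which higher is worse. A range bounded on both sides would not prove direction alone, but it agrees with Step 1.

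**Step 5. Construct**

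Item 1 asks about symptom frequency. Items 2 to 20 each name a symptom or sensitivity, such as grittiness, burning, blurred vision, redness, light sensitivity or headache. None refers to treatment or satisfaction.

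**The case against.** The strongest reply is that nothing computed goes wrong. The formula beside the clause is correct, no visible derivation for this score uses direction (no responder cut-off, no ranking, no imputation), and the analysis is descriptive. The direction can also be worked out elsewhere: from the words Symptom Bother in the scale's name, from the response labels, and from the entry range that sites apply to every Group 1 subject. An author would have to overlook all three to invert the result. The table shells are a separate document that has not been seen and may already carry a correct footnote. On this view the point is a minor inconsistency of wording.

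Most of this stands as a limit on the harm. No output value is affected, misreading is possible rather than certain, and no fault can be claimed in the shells or in the redacted part of SAP 5.3. The absence of direction from the listed table titles proves little, since a title need not state it.

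It does not rescue the clause. Direction is inferable elsewhere, but the clause is the only explicit visible statement of it, and it is wrong. Redaction does not explain the conflict, because the sentence, the codes and the formula are all fully visible. A pre-specified plan should not need its reader to overrule its own description of a primary endpoint, and a direction corrected only after results are known is harder to defend.

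**Conclusion.** The concern holds on both counts. By the SAP's own scoring, IDEEL-SB runs from 0 (best) to 100 (worst), so SAP 5.3.1 has the direction reversed. It also names a construct that the questionnaire does not measure.

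The effect on computed results is nil: scores, means, confidence intervals, eligibility and sample size are unchanged. The effect on interpretation, if the clause is followed, is a reversed sign for any change in the Group 1 primary endpoint. Group 2 and the safety endpoints are not touched.

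The conclusion rests only on the visible coding and formula; the 25-point example rests on assumed answers and only illustrates the reversal. This should be fixed before the results are written up, because it concerns a primary endpoint in a study whose effectiveness reading depends on direction.

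**What to change.** - In SAP 5.3.1, replace the clause with: *Scores range from 0 to 100; a higher score indicates greater symptom bother (worse), and a lower score at Visit 3 than at Baseline indicates improvement.*
- Put the same statement in the footnotes of Tables 14.2.1.1.1.1 and 14.2.1.1.1.2, and use it in the study report.
- In the same edit, correct the reference to Appendix 13.2 so that it points to 12.2.
- As a precaution, check once that the table shells and any direction-dependent derivation follow the corrected statement.

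The cost is one sentence, two footnotes, a cross-reference and one check. No analysis, data collection or study procedure changes, and there is no downside.

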2.1. Full Analysis Set (FAS)

The FAS will include all subjects/eyes exposed to at least one dose of Systane Ultra PF. The FAS will serve as the primary analysis set for all effectiveness and safety analyses.

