3.2. Rules for Reporting Statistics

Continuous variables will be summarized using descriptive statistics, i.e., by the number of non-missing observations (n), mean, standard deviation (SD), first quartile (Q1), median, third quartile (Q3), minimum and maximum. Where specified in the table shells, the number of missing observations and 95% CI for the mean will also be provided.

For reporting conventions:

- The number of non-missing and missing observations will be presented as whole numbers.
- The minimum and maximum will be presented with the same number of decimal places as presented in the data.
- The mean (and correspondent 95% CI), median, Q1 and Q3 will generally be displayed with one more decimal place than presented in the data.
- The SD will generally be displayed with 2 more decimal places than the raw data. If there is only one observation (n=1), the SD will be displayed as a hyphen ("--").
- If there is no observation, summary statistics will be displayed with a hyphen ("--").

Qualitative variables will be summarized by frequency counts (n) and percentages (%). Unless otherwise stated, the calculation of proportions/percentages for a given qualitative variable will exclude subjects/eyes with missing values from the denominator.

For reporting conventions, percentages will be reported to one decimal place unless greater precision is deemed appropriate, except for cases when 100% is presented. In cases of a count of 0, the percentage will not be presented.

In case the analysis refers only to certain visits/timepoints, summary statistics and percentages will be based on the number of subjects/eyes having available result at each visit/timepoint.

Summaries on change from Baseline by visit/timepoint will be based on subjects/eyes who have both baseline and post-baseline values at the visit/timepoint being summarized.

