6.3.2. BCVA

BCVA will be assessed per standard practice at the Screening/Baseline visit (Day 1) and at Visit 3 (and at unscheduled and early exit visits, as necessary).

For each eye, the distance visual acuity (VA) will be collected as per the site's standard of care practice using charts validated for the specific testing distance, which may include for example, 6 m for Snellen chart, 20 ft for Snellen chart, decimal chart and logMAR score. The values for BCVA will be presented in logMAR. BCVA will be summarized as a continuous variable at each analysis visit (Baseline and Visit 3) [eye-level summary]. The mean BCVA score will be presented together with the corresponding 95% CI. In addition, the change from Baseline will be summarized at Visit 3.

A supportive listing for BCVA assessments will be provided.

Derivations:

- BCVA (logMAR) = $-\log_{10} (20 / \text{Snellen VA 20 ft fractions})$ if measured in 20 ft for Snellen chart.
- BCVA (logMAR) = $-\log_{10} (6 / \text{Snellen VA 6 m fractions})$ if measured in 6 m for Snellen chart.
- BCVA (logMAR) = $-\log_{10} (\text{decimal acuity})$ if measured in decimal chart.

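### The visible SAP 5.3.1 gives a mean IDEEL-SB score per visit for Group 1 but no within-subject change; confirm that a paired change is planned, or add one.

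*SAP*

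**What the plan says.** SAP 5.1 defines the endpoint as a score at two time points: "Group 1: Dry eye (DE) questionnaire via IDEEL-SB at Baseline and at Visit 3". SAP 5.3.1 then treats it as a continuous variable, summarised "at each analysis visit (Baseline and Visit 3). The mean IDEEL-SB score will be presented together with the corresponding 95% CI". The visible Group 1 paragraph ends there, with no redaction mark after that sentence.

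Four other rules decide who is counted and how:

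- SAP 2.1 on the analysis set: "The FAS will include all subjects/eyes exposed to at least one dose of Systane Ultra PF".
- SAP 3.2 on by-visit summaries: "summary statistics and percentages will be based on the number of subjects/eyes having available result at each visit/timepoint".
- SAP 5, introduction, on missing data: "No imputation for missing values will be carried out for the primary and supportive effectiveness analyses".
- SAP 3.2 on change summaries: "Summaries on change from Baseline by visit/timepoint will be based on subjects/eyes who have both baseline and post-baseline values". This says how a change is computed, not which endpoints get one.

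For BCVA, a safety endpoint, SAP 6.3.2 does order a change: "In addition, the change from Baseline will be summarized at Visit 3". SAP 6.3.3 also orders Baseline-to-Visit 3 shift tables for biomicroscopy.

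**The concern.** The study has one arm and no comparator, and its objective is to assess performance. Readers will therefore look for how much the score moved between Baseline and Visit 3. Two means, each with its own interval, do not answer that well, for two reasons.

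First, the precision of the change depends on the within-subject correlation, which the visit summaries do not show. Second, a subject who was dosed at Baseline but has no Visit 3 score counts in the Baseline mean only. If such subjects started at a different level, the difference between the two means moves even when nobody's score has changed.

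No error rate or sample size is at stake, because the study tests no hypothesis. What is at stake is how well the report describes the size and precision of the change.

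**Working it through.** **The plan's own precision figure.** SAP section 8 gives precision for proportions only. With 54 subjects and an expected proportion of 0.0543, the half-width is 1.96 × √(0.0543 × 0.9457 / 54) = 0.0604, which agrees with the stated 0.060. All eight cells of SAP Table 3 also reproduce. No precision is stated for the IDEEL-SB mean or its change.

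**Inputs.** The target is 27 evaluable subjects in Group 1 (Protocol 6.4.1, SAP section 8). The documents give neither the SD of the score nor the correlation r between visits. Results are therefore in SD units, over an assumed range r = 0.3 to 0.7.

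**Precision with 27 subjects (t quantile, 26 degrees of freedom)**

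- One visit mean: t(0.975, 26) / √27 = 0.396 SD, whatever r is.
- Two visits combined as if independent: √2 × 0.396 = 0.559 SD.
- Paired change with equal SDs: 0.396 × √(2(1 − r)).

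| Assumed r | Paired half-width (SD) | Independent / paired = 1/√(1 − r) |
|---|---|---|
| 0.3 | 0.468 | 1.20 |
| 0.5 | 0.396 | 1.41 |
| 0.7 | 0.306 | 1.83 |

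In score points, at r = 0.3, 0.5 and 0.7, an assumed SD of 10 gives half-widths of 4.7, 4.0 and 3.1. An assumed SD of 20 gives 9.4, 7.9 and 6.1.

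The entry range limits the Baseline score only, so the SDs may differ. Let k be the Visit 3 SD divided by the Baseline SD. The paired half-width is then 0.396 × √(1 + k² − 2rk) Baseline SD. With k assumed between 0.75 and 1.25, it runs from 0.28 (k = 0.75, r = 0.7) to 0.53 (k = 1.25, r = 0.3).

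**Who is in each mean.** Suppose 27 subjects have both scores and m dosed subjects have Baseline only. Let D be the Baseline mean of those m minus that of the 27. The all-dosed Baseline mean exceeds the paired-subset Baseline mean by D × m / (27 + m), so the difference of the two visit means is off by that amount in the opposite direction.

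- m = 0: no shift.
- m = 3: 3/30 = 0.10 × D.
- m = 7: 7/34 = 0.21 × D.

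The last case is an upper one. It assumes that the 68 recruited split evenly, that all 34 in Group 1 are dosed, and that there are no screen failures. The documents give neither the sign nor the size of D, so these are multipliers and not estimates of bias.

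**Direction of the score.** SAP 5.3.1 says that a higher score means more satisfaction and less bother. The item scoring in Protocol 7.3.3.1 and SAP Appendix 12.2 runs from 0 (symptom absent) to 4 (bothered very much), and the score is the item mean × 25. A higher score therefore means more bother. The sign of a Visit 3 minus Baseline change would be misread until SAP 5.3.1 agrees with the scoring.

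**The case against.** The strongest reply is that absence cannot be shown. A large block after the derivations in SAP 5.3.1 is blacked out, and the table shells are a separate document. The title of Table 14.2.1.1.1.1 does not rule out a change row, because the BCVA table title has the same form and BCVA does get a change summary. This stands, and it is why the request is to confirm or add.

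The plan also delivers what it defines: the score at two visits, described without a hypothesis. A reader might infer that the primary analysis is wrong or incomplete against its own endpoint. The documents do not support that.

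A reader might also infer that the two means come from two distinct samples. They do not. Group 1 subjects need a Baseline IDEEL-SB score to be eligible, so the Visit 3 subjects are in practice a subset of the Baseline subjects.

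There are mitigations. Each visit summary shows its n, the disposition table gives discontinuations with reasons, and Listing 16.2.4.1 lists the questionnaire. Someone holding the full report could derive the changes. That helps, but it does not put the change and its interval in the summary table.

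Finally, an interval for change in a single-arm study that selects on the Baseline score invites an efficacy reading that regression to the mean could produce. That is a fair warning about the fix, and a caveat should go with it.

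**Conclusion.** The point holds as a cheap improvement, limited to the visible text for Group 1. With 27 subjects, each visit interval has a half-width of 0.40 SD. The paired change has 0.47, 0.40 or 0.31 SD at assumed correlations of 0.3, 0.5 or 0.7 with equal SDs. A reader who combined the two visit intervals as independent would get 0.56 SD, although the SAP does not propose that step. The correlations and the SD ratio are assumptions.

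The effect of subjects without a Visit 3 score is possible but cannot be sized. It would be wrong to infer a 21% bias from the 7-of-34 case, because that is a multiplier on an unknown Baseline gap.

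The point does not carry over to CLDEQ-8 in Group 2 without a condition, because a redaction follows directly after the corresponding sentence there.

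**What to change.** 1. Confirm that SAP 5.3.1 and Table 14.2.1.1.1.1 include the mean within-subject change, Visit 3 minus Baseline, with a 95% t interval in subjects with both scores under the existing SAP 3.2 rule. If they do not, add it.
2. Show the Baseline mean of that same subset next to the all-dosed Baseline mean.
3. Do the same for CLDEQ-8 in Group 2 only if the redacted text does not already do so.
4. Correct the direction sentence in SAP 5.3.1 to match the item scoring, so that a negative IDEEL-SB change reads as less bother.
5. Note with the table that the change is descriptive and applies to subjects with a Visit 3 score. It may reflect regression to the mean, since entry is by Baseline score and there is no control arm, and pairing does not remove bias from outcome-related dropout.

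The cost is some SAP wording and a few extra table rows from data already collected. The protocol, the endpoint and the no-imputation rule stay as they are.
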